7.4 Blinding and masking

The blinding will correspond to the research subject and the principal investigator. In addition, the statistical analysis will be carried out in a blinded manner in the case of a partial and final analysis.

The masking will be carried out using boxes in the identical primary packaging in the two groups and re-labeling the bottles of both interventions.

Blinding for the research subject and the researcher will be done by replacing the commercial labels in the case of the comparator in the bottles and the use of identical labels that contain the assignment number.

7.4.1 Opening of blinding

Blinding may be opened in the following cases:

1. Presence of a serious adverse event.
2. Safety alarm due to the use of the drugs under study.
3. In case the sponsor determines it for any reason of security or another reason that considers pertinent.

8. Methods Collection, administration and data analysis

8.1 Methods of data collection

A clinical monitor will be assigned to each research center, which will be authorized to monitor, review, procure and ensure that the quality of the information obtained from the participants is reliable and trustworthy. Each monitor will schedule periodic visits to the research centers in order to review the source documents and corroborate the information captured in the CRF. All clinical monitors will be trained in relation to the information of the study protocol (objective, visits, procedures, range of accepted values, etc.). In the event that the data are not identical between the two registers, the clinical monitor will generate a discrepancy, which must be resolved by the research center in time that the sponsor deems reasonable to meet the objectives of the clinical study. The correction of the discrepancies will be made according to the Good Documentation Practices.

The data registered in the CRF will be reviewed by personnel of Sophia Laboratories, trained in the ophthalmological, clinical and pharmacological area, which will be able to generate discrepancies in the event that the data do not comply with the stipulations of the research protocol or put the participants at risk.

Once all discrepancies generated by the team of clinical monitors and clinical staff have been resolved, the data will be downloaded into an electronic database (Excel Sheet) by personnel designated by the sponsor. A new review of the data will be carried out to corroborate the fidelity of the same and new discrepancies may be generated in case it was considered.

The database generated will be safeguarded by the sponsor and will only have personal access designated by the same.

8.1.1 Strategies to complete the follow-up

- You will be informed in a clear way the importance of the study and the benefits that the population will obtain from the results of the study.

- Transportation assistance will be provided in order for the participant to attend their visits.
- A printed calendar will be provided with the objective of reminding the participant of their appointments and the activities that will be carried out, in addition to the estimated duration of the same.
- In case the participant does not attend his / her appointment, the research center must make a call to know the reason and try to arrange a new appointment within the established window period or an unscheduled appointment.
- In case it is not possible to make an appointment, it will be asked about the presence of adverse events and the reason for leaving the study, as minimum data.

8.2 Data management

The subject's medical record (including clinical notes, test results, etc.), as well as the subject's diary, are considered source data.

The IP or the designated person of your team will fill out the Case Report Format (CRF) as well as all other documents provided by the sponsor (for example: documents related to the management of the treatment).

An electronic CRF was designed to record the data that are required in the protocol and that the researcher collects in each of the visits.

In the case of self-assessment questionnaires, it is not permissible for the principal investigator or person responsible for filling in to modify what was written by the subject of the study.

The data capture in the research site will be done by the researcher or the designated person of his team after performing the Medical File. The researcher or a designated person of your team will be trained in filling the CRF.

All corrections to the CRF data should be made by the investigator or the designated person of your team in accordance with the instructions provided.

To ensure the confidentiality and security of the data, user names and access codes will be used to restrict access to the system only to authorized personnel.

The monitor must ensure that all the data has been filled in the CRF. After comparing the data against the source documents, the monitor will ask the researcher to make the necessary correction / clarification, so that they are answered and closed as quickly as possible.

The Scientific Committee of Laboratories Sophia S.A. of C.V. will give the latest medical-scientific review, and will set the standard for freezing the database.

8.3 Statistical methodology

8.3.1 Analysis of primary and secondary outcome variables

The statistical analysis will be carried out by personnel of Sophia Laboratories. The statistical program SPSS version 19 will be used.

The designated personnel will be blinded to the intervention groups. The coding will be done using consecutive numbers for each intervention group.

The data will be collected and sorted in an excel sheet. Later they will be exported to the platform of the SPSS program. The variables will be categorized according to their nature.

The results of the continuous quantitative variables will be presented in measures of central tendency: mean, standard deviation and ranges. See **Table 5 Variable measurement method**. The total size of the samples will consider an eye as a case for the evaluation of the efficacy.

The normal distribution of results will be obtained through the Kolmogorov-Smirnov and Shapiro-Wilks test, as applicable.

The statistical analysis of the continuous quantitative variables to find significant differences (p) will be the following:

. Inter-group analysis: t test for paired samples.

. Intra-group analysis: Mc Nemar test. Cellularity assessments in the anterior chamber will be considered for the analysis before the application of the intervention and in the final visit. The level of difference to consider significance will be of an alpha of 0.05 or less.

The result of nominal and ordinal qualitative variables will be presented in frequencies, proportions and percentages. See **Table 5 Method for measuring variables**

The statistical analysis to identify significant differences of the qualitative variables will be done by creating 2x2 contingency tables and will be done as follows:

- Difference between groups: χ^2 test (Chi-square) of Pearson or Fisher's exact in expected values less than 5.
- Intra-group analysis: Mc Nemar test.

The level of difference to consider significance will be an alpha of 0.05 or less.

For the reporting of adverse events all eyes of those participants who were randomly assigned to an intervention group will be considered. The results will be expressed in number of cases.

The final report of the results will be shown in tables or graphs, as appropriate.

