
Reference product, dose and route of administration:
 
1. Prednefrin® SF. Prednisolone Acetate 1%. Prepared by Allergan, S.A. of C.V.
 
- Dosage: 1 drop 4 times a day (every 4 hours) during the period of vigil in the operated eye, for 14 days. Dose reduction for 14 days at the discretion of the principal investigator.- Route of administration: topical ophthalmic

Evaluation criteria:
 
Effectiveness:
 
 • Primary 
 o Cellularity in the anterior chamber • Secondary 
 o Visual capacity (CV) o Central thickness of the retina or Clinical corneal edema or conjunctival hyperemia or Flare o Symptomatology 
 - Pain - Photophobia 
Tolerability:
 
 • Post-Stretching Ocular Symptomatology 
Security:
 
 • Visual capacity (CV) • Adverse events (EA) • Intraocular pressure (PIO)

Statistical methodology:
 
The result of the continuous quantitative variables will be presented in measures of central tendency: mean, standard deviation and ranges. The total size of the samples will consider an eye as a case for the evaluation of efficacy.
 
The normal distribution of the results will be obtained through the Kolmogorov-Smirnov and Shapiro-Wilks test. The statistical analysis of the continuous quantitative variables to find significant differences (p) will be in the inter-group analysis: t test for paired samples; for intra-group analysis: McNemar test. Evaluations of cellularity in the anterior chamber before the application of the intervention and in the final visit will be considered for the analysis. The level of difference to consider significance will be an alpha of 0.05 or less. The result of nominal and ordinal qualitative variables will be presented in frequencies, proportions and percentages. The statistical analysis to identify significant differences of the qualitative variables will be done creating 2x2 contingency tables and will be carried out as follows: Difference between groups: χ^2 test (Chi-square) of Pearson or Fisher's exact in expected values less than 5 ; for intra-group analysis: McNemar test

Page left intentionally blank

2. Content

1. SUMMARY	1
2. CONTENT	5
3. ABBREVIATION INDEX	9
4. ADMINISTRATIVE STRUCTURE OF THE STUDY	11
5. INTRODUCTION	13
5.1 THEORETICAL FRAMEWORK	13

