5.5.4 Hypothesis

H0: The use of the ophthalmic emulsion PRO-145 is not effective when decreasing the inflammatory response evaluated by means of cellularity in the anterior chamber, after phacoemulsification.

Ha: The use of the ophthalmic emulsion PRO-145 is effective in decreasing the inflammatory response evaluated by means of cellularity in the anterior chamber, after phacoemulsification.

5.6 Design and plan of the study.

Phase III clinical trial, parallel, controlled, randomized, double blind. Participants will be postsurgical phacoemulsification patients, who will be randomly assigned to 2 intervention groups with steroidal anti-inflammatory drugs. One group will receive the PRO-145 test formulation and the other group will be exposed to prednisolone acetate 1%.

[figure not shown]

Figure 2. Study design.

5.6.1 Discussion of the study design.

In clinical research it is common to propose trials with the objective of evaluating the efficacy of a product under investigation against a reference medicine or active control, in order to compare the new product under investigation from a clinical or statistical point of view to a drug commercially available

The clinical trial is the ideal model to evaluate the effectiveness of two interventions, it allows obtaining the highest quality evidence among different types of research. The characteristics of randomization and double blind, allow to avoid biases (selection, evaluation, etc.) that can not be avoided with other models. Being controlled and parallel groups allows distinguishing the effects of interventions in isolation.

The proposed clinical trial aims to evaluate the efficacy, safety and tolerability profile of a formulation of DFBA 0.05% and compare it against the safety, tolerability and efficacy profile of commercially available steroid administration, and widely used for its efficacy profile and known security.

6. Material and methods. Participants, interventions and variables.

6.1 Study Center.

The present study will be performed in ophthalmology offices duly equipped and registered for their proper functioning. According to the needs of the sponsor, these may be private or public, be attached to a hospital or clinic or be independent.

This is a multicentre study that is intended to be carried out in Guadalajara, Mexico City and Monterrey.

6.1.1 Organization of the center.

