There is no standardized parameter to define an adequate adherence, it must be defined and outlined by the objectives of the research in particular. [62] The efficacy of ophthalmic steroids is based on two fundamental principles: 1) The specific type and location of the inflammation determines the appropriate route of administration and 2) The treatment should be instituted as soon as possible, and the dose should be high enough and administration frequent enough to suppress inflammatory activity. According to the therapeutic utility curve, to establish the limits of the therapeutic window, a dosage regimen is required in which 50% of the established doses are exceeded, in order to achieve a pharmacological effect. A therapeutic regimen below this value is expected a lack of efficacy. Therefore, an adherence of over 60% according to the weight of the bottle ensures that it remains within the limits of efficacy of the therapeutic window established in the protocol. [64] [65] [66] For the efficacy analysis, only subjects with a minimum adherence of 80% by means of the subject's daily tool and a minimum of 60% by the weight of the bottle will be considered. The variation in the percentage of the measurement method has been chosen empirically to counteract the sensitivity and specificity of the same. It is estimated that with a minimum adherence of 60% the intervention can exert its expected anti-inflammatory pharmacological action. [44]

6.3.3 Treatments and concomitant interventions allowed and prohibited before and during the study.

The subjects admitted correctly to the study, who meet the eligibility criteria, may continue with the systemic treatment of the underlying diseases. If during the development of the study they require the implementation of a new permitted medication, they may do so. All concomitant medications used must be duly reported in the notes of the clinical file and in the corresponding section.

Allowed medications:

- Ophthalmic:
- All permitted medications applied via ophthalmic during the study, must wait a minimum period of 10 minutes from the last application of the treatments under study or reference. The foregoing in order to avoid the interaction of the treatments in the tear film, based on the tear flow index and the physiological tear volume. [67]
 - Tetracaine 0.5%
 - Tropicamide 0.8% / Phenylephrine 5%
 - Any antibiotic
 - Beta-blockers
 - Alpha agonists
- Administered by a different route to ophthalmic:

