6.5.3 Diagram of the study

[figure not shown]

Figure 4. Diagram of the study

6.6 Sample size.

The sample size calculated for the present study is 178 subjects.

Divided into two intervention groups, each group will be comprised of 89 subjects. Each subject will provide an eye for efficacy analysis.

6.6.1 Calculation of the sample size.

The sample size was calculated using the formula for two proportions variables as well as the data was entered into the online calculator, software developed in: www.powerandsamplesize.com based on Chow S et al. [72]

With a statistical confidence of 95% corresponding to the type I error, equal to 1.96, with a power of 80%, corresponding to the type II error, equal to 0.84. A 78.9% efficiency ratio was considered in the reduction of the degree of cells in the anterior chamber after the application of 4 weeks of difluprednate 0.05% in 79 subjects submitted to phacoemulsification compared to an efficiency ratio of 77.5% with the use of 1% prednisolone. [53]

According to the previous calculation, the result is 74 eyes per group. The total when considering 2 intervention groups is 148 eyes, which was increased by 20% (30 eyes) for the probable losses. The total sample size required is 178 eyes. **Total n = 178 eyes.**

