8.3.3 Population analysis and management of missing data

The effectiveness analysis will consider those cases in which the measurements of the baseline and final visit are met. Those subjects who do not comply with any of these measurements will not be integrated into the final database to evaluate the effectiveness. Nevertheless, an intention to treat analysis (ITT) will be carried out.

The safety assessment will include in the analysis all those subjects (considering one eye or both) who have been exposed at least once to any of the interventions regardless of the visit in which they were eliminated from the study.

9. Methods Monitoring

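### The tests named for the three continuous variables do not fit the design: a paired t test between independent arms, and McNemar within arm

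*Combined protocol and SAP*

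**What the plan says.** Section 8.3.1 deals with continuous and qualitative variables separately. Under continuous variables it gives "Inter-group analysis: t test for paired samples" and then McNemar for the intra-group analysis. Immediately after the McNemar entry it says: "Cellularity assessments in the anterior chamber will be considered for the analysis before the application of the intervention and in the final visit". The statistical paragraph of the Summary repeats the pair of tests: "inter-group analysis: t test for paired samples; for intra-group analysis: McNemar test".

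Qualitative variables get Pearson chi-square or Fisher between groups and McNemar within group, on 2x2 tables. Anterior chamber cellularity, the primary variable, is ordinal in Table 5 and belongs there.

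Section 5.6 describes the design as "Phase III clinical trial, parallel, controlled, randomized, double blind", and section 6.6 adds "Each subject will provide an eye for efficacy analysis". Section 8.3.1 plans normality tests but names no test to use if normality fails.

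**The concern.** A paired t test analyses differences within matched units, and here no unit in one arm is matched to a unit in the other. The software will still pair row 1 with row 1, so the p-value depends on how the file was sorted. Section 8.3.1 has the data sorted in a spreadsheet but gives no sort key, so a second analyst could not be sure of reproducing the result. The test also discards every subject left without a row partner. Exact equality of the arms is unlikely in the efficacy set, which is restricted twice: "The effectiveness analysis will consider those cases in which the measurements of the baseline and final visit are met" (section 8.3.3), and "For the efficacy analysis, only subjects with a minimum adherence of 80"% by diary and 60% by bottle weight (section 6.3.2).

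McNemar compares discordant yes/no pairs and cannot be run on mmHg, microns or decimal acuity without a cut-point.

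Three distinct variables are affected. IOP and visual capacity are two of the three primary safety variables (6.4.1.1); visual capacity and retinal thickness are two of the six secondary efficacy variables (6.4.2.2). Section 5.3.1.5 itself recognises a rise in IOP as a risk of topical steroids.

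**Working it through.** **1. Could pairs exist?** The design is parallel (5.6) with one eye per subject (6.6). Earlier participation with the other eye is an exclusion (6.2.2.1), and treatment goes only into the operated eye (6.3.1). No matching is defined anywhere.

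**2. Could McNemar be run?** Its statistic is (b − c)²/(b + c), where b and c count subjects who change from yes to no and from no to yes. Table 5 gives the three variables in decimals, microns and mmHg, and no section defines a yes/no version. Section 8.3.2 plans an analysis of changes between visits but names no test.

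**3. How often would the arms finish equal?** The only relevant figure in the plan is the loss allowance in 6.6.1: 148 eyes, "which was increased by 20% (30 eyes) for the probable losses". This reproduces: 148 × 1.20 = 177.6, rounded to 178, or 89 per arm. Assume each subject completes independently with probability 148/178 = 0.8315:

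- Expected completers per arm: 89 × 0.8315 = 74.
- Variance per arm: 89 × 0.8315 × 0.1685 = 12.47.
- SD of the difference between arms: √(2 × 12.47) = 4.99.
- Mean absolute difference: 4.99 × √(2/π) ≈ 4.0 subjects.
- Probability of equal arms: about 1/(4.99 × √(2π)) = 0.08.

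**4. How far does row order move the p-value?** Take n = 74 per arm and equal SDs. If r is the chance correlation created by arbitrary pairing,

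t(paired) = t(independent) / √(1 − r).

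Over random row orders r has mean 0 and SD 1/√73 = 0.117. The two-sided 5% critical values are 1.993 (73 df, paired) and 1.976 (146 df, independent). The paired test is significant when r > 1 − (t/1.993)², with t the independent statistic. For a correct p of 0.05, t = 1.976, so r must exceed 1 − 0.983 = 0.017. That is 0.017/0.117 ≈ 0.14 SD, and the chance is about 0.44. Simulation with 20,000 row orders per fixed dataset agrees:

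| Correct two-sample p | Row orders with paired p<0.05 |
|---|---|
| 0.02 | 99.96% |
| 0.03 | 96% |
| 0.04 | 75% |
| 0.05 | 45% |
| 0.06 | 21% |
| 0.08 | 3% |
| 0.10 | 0.4% |

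At a correct p of 0.05, the paired p ranges from 0.021 to 0.088 across 99% of row orders.

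**5. Error rates over whole trials.** Normal data with SD 1, two-sided alpha 0.05, losses as in step 3, 100,000 trials per row. The paired test uses as many rows as the smaller arm has. The plan gives no SD or target difference for these variables, so the effect sizes are assumptions; 0.464 SD gives 80% power at 74 per arm.

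| True difference | Independent t rejects | Paired t rejects | Verdicts differ |
|---|---|---|---|
| 0 | 5.0% | 4.9% | 1.7% |
| 0.33 SD | 51.5% | 50.0% | 6.2% |
| 0.464 SD | 79.9% | 78.2% | 4.8% |

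No size can be put on the within-arm fault, because the named test cannot be run.

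**The case against.** The best case on the other side is that little depends on this numerically. Type I error is unchanged and the power loss is under 2 points. In one simulated dataset with an independent p of 0.158, the paired p stayed between 0.074 and 0.232 over 5,000 re-pairings and never reached 0.05. The primary comparison and the sample size do not use these tests. That all stands and limits the claim. It does not make the tests usable: one has no pairs to work on and the other has no binary data.

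The McNemar line may be misplaced, since the sentence after it concerns cellularity. That is plausible. On that reading no within-arm test is named at all for the continuous variables. This gap matters because the objectives in 5.5.3 are worded product by product, so the within-arm change is literally what they ask about.

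The text is visibly translated, and the labels may have been swapped. Swapping them would put the paired t test within arm, which is right, but McNemar between arms, which is still invalid. The same wording also appears in two places.

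Finally, the loss model in step 3 describes efficacy completers. The safety set in 8.3.3 is everyone exposed at least once, so the 8% and 4-subject figures do not carry over to IOP and visual capacity as safety variables. Row-order dependence does, because it arises even with equal arms.

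**Conclusion.** The concern holds. As written, none of the three continuous variables has a valid test, either between arms or within arm, and no other section supplies one. The between-arm fault makes the p-value arbitrary near the threshold: it decides significance mainly when the correct p is roughly 0.03 to 0.08, and it costs 1.5 to 1.7 points of power in the cases examined. It does not inflate type I error. The means, SDs and ranges, and the primary chi-square or Fisher comparison of cell elimination, are untouched.

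The figures assume normal data, equal SDs, independent losses at the plan's own allowance and the stated effect sizes. The mismatch between test and design needs none of these assumptions. The correction is needed because pre-specified analyses of primary safety variables cannot be carried out validly as described, not because a large bias is expected.

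**What to change.** Before unblinding, replace the continuous-variable tests in section 8.3.1 and in the Summary with wording such as:

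> Continuous variables (visual capacity, central retinal thickness, IOP). Between arms: independent-samples t test, or Mann-Whitney if the planned normality tests fail. Within arm, baseline to final visit: paired t test, or Wilcoxon signed-rank if non-normal. McNemar and chi-square or Fisher are used only for binary outcomes, such as elimination of anterior chamber cells.

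Move the cellularity sentence out of the continuous-variable list.

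A related gap can be closed in the same edit. Table 5 types symptomatology as discrete, so the pain and photophobia scores fall under neither list in 8.3.1. Name a test for them, for example Mann-Whitney between arms and Wilcoxon signed-rank within arm.

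The cost is one protocol amendment, with committee approval and regulatory authorisation under section 10.2. It needs no new data, no extra visits and no change to the sample size.

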5.5.2 Specific objectives

- Evaluate the efficacy of PRO-145 through the elimination of anterior chamber cellularity (CCA) at the final visit.
- Evaluate the efficacy of prednisolone acetate 1% by means of the elimination of CCA in the final visit

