5.5.3 Secondary objectives

- Evaluate the efficacy of PRO-145 through the decrease of CCA in the ordinal scale during visits
- Evaluate the efficacy of PRO-145 by decreasing the central thickness of the retina (GCR).
- Evaluate the efficacy of PRO-145 by decreasing clinical corneal edema.
- Evaluate the efficacy of PRO-145 through the reduction of conjunctival hyperemia.
- Evaluate the efficacy of PRO-145 by means of the decrease of flare.
- Evaluate the efficacy of PRO-145 in reducing symptoms: pain and photophobia.
- To evaluate the tolerability of PRO-145 by means of the interrogation of ocular symptomatology post-stiffening.

- Evaluate the safety of PRO-145 through the CV, the PIO and the incidence of EA
- To evaluate the efficacy of prednisolone acetate 1% by means of the decrease of CCA in the ordinal scale during visits
- Evaluate the efficacy of prednisolone acetate 1% by means of the decrease in GCR.
- Evaluate the efficacy of prednisolone acetate 1% by means of the decrease of clinical corneal edema.
- Evaluate the efficacy of prednisolone acetate 1% by means of the reduction of conjunctival hyperemia.
- Evaluate the efficacy of prednisolone acetate 1% by means of the decrease in flare.
- Evaluate the efficacy of prednisolone acetate 1% in reducing symptoms: pain and photophobia.
- To assess the tolerability of prednisolone acetate 1% by means of the interrogation of ocular symptomatology postinstillation.
- Evaluate the safety of prednisolone acetate 1% by means of the CV, the PIO and the incidence of EA.

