Subsequently the best refractive correction of the subject will be made and the examination will be repeated using the obtained refraction. This result will be reported as visual capacity (CV), it will be recorded as a fraction in the clinical file and in the CRF, and in the CRF it will be written in decimal. By definition, the CV can not be inferior to the AV.

6.4.3.3 Evaluation of adverse events.

The evaluation of adverse events requires a questioning conducted by the IP and the appropriate exploratory techniques for its detection.

The IP will record in the corresponding section of the CRF the EAs that the subjects of the study will present.

The management of the EAs will be done according to what is described in section 9.3 Adverse events.

6.4.3.4 History of symptomatology.

The subject will be questioned directly about the presence in general (since the last visit) of the following symptoms: pain and photophobia. Respond about the severity and frequency of symptoms such as:

Severity: Absent (0), very mild (1), mild (2), moderate (3) and severe (4)

Frequency: At all times (4), almost at all times (3), 50% of the time (2), almost at no time (1), at any time (0).

The number corresponding to each symptom will be registered in the CRF.

Symptomatology postinstillation:

The subject will be questioned if after applying the medication he felt burning, pruritus, a foreign body sensation and blurred vision.

Presence or absence: it will be marked as present (1) or absent (0) in the CRF for each of the symptoms questioned

Frequency: In all applications (4), almost in all applications (3), 50% of applications (2), almost in no application (1), in no application (0)

Duration: More than 5 minutes after the application (3), More than one minute but less than 5 (2), Less than one minute (1), Nothing (0).

The frequency and duration is for all the symptoms in general, the highest frequency and duration reported will be reported in the CRF.

6.4.3.5 Optical coherence tomography.

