6.7 Recruitment

The subjects will be recruited from the outpatient IP consultation and who have met the criteria for cataract surgery by phacoemulsification. The IP may include subjects who are not operated on their own, as long as the surgeon responsible for the surgery hands over the postoperative management to the IP and its equipment.

7. Methods Assignment of the intervention

7.1 Generation of the allocation sequence.

2 strata corresponding to the intervention groups will be used, which will be balanced for each research center. The allocation will be 1: 1. The generation will be done through an electronic system validated by an external provider, previously evaluated and authorized by Sophia Laboratories S.A. of C.V. The information corresponding to this provider will be found in the master folder of the study.

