8.3.2 Additional analyzes

An internal analysis will be made to know the changes that occur between each visit. It is the sponsor's prerogative to request an additional analysis of the data, during the conduction of the study or at the end of this.

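### Ordinal secondary outcomes are collapsed to 2x2 tables with no cut-point or definition of decrease; one prespecified whole-scale ordinal test would remove the open choice

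*Combined protocol and SAP*

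**What the plan says.** Table 5 (section 6.4.3) types anterior chamber cellularity (CCA), flare, corneal edema and conjunctival hyperemia as ordinal. Table 6 gives CCA six grades and Table 7 gives flare five.

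Section 8.3.1 treats nominal and ordinal variables together, points to Table 5, and says: "The statistical analysis to identify significant differences of the qualitative variables will be done by creating 2x2 contingency tables". The between-group test is Pearson's chi-square, or Fisher's exact when expected counts are small. The within-group test is McNemar. Significance is 0.05 for each.

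The objectives do not supply the missing cut:

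- Section 5.5.3 states the CCA secondary as "Evaluate the efficacy of PRO-145 through the decrease of CCA in the ordinal scale during visits". Flare, edema and hyperemia are likewise framed as a decrease or reduction, for each arm separately.
- Section 8.3.2 adds only "An internal analysis will be made to know the changes that occur between each visit".
- Only the primary implies a cut. Section 5.5.2 reads "Evaluate the efficacy of PRO-145 through the elimination of anterior chamber cellularity (CCA) at the final visit", which is grade 0 against any higher grade.

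Pain and photophobia each get a severity score and a frequency score, both 0 to 4 (section 6.4.3.4). Table 5 types symptoms as discrete, whereas 8.3.1 has rules only for continuous and for nominal or ordinal variables.

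On allocation, section 7.1 says "2 strata corresponding to the intervention groups will be used, which will be balanced for each research center". Section 8.3 names no centre term.

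**The concern.** A five- or six-grade scale becomes a 2x2 table only once someone picks a cut. A decrease could mean reaching a given grade, or dropping some number of steps from baseline. The eligibility criteria (section 6.2) set no minimum baseline CCA grade, so an eye at grade 0 at baseline cannot decrease, and no rule says how it counts. McNemar has the same gap, and it is the test closest to the single-arm wording of section 5.5.3.

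Two things are at stake. Power for the same data and the same true effect depends on the cut. And if the cut is settled after results are seen, the nominal 5% no longer holds. Collapsing the scale also fits poorly with an objective stated on the ordinal scale.

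**Working it through.** **1. Inputs.** From the plan: 74 evaluable eyes per arm, and rates of 78.9% and 77.5% (section 6.6.1); two-sided 0.05; Pearson, or Fisher when an expected count is below 5 (section 8.3.1). The plan gives no grade distributions, so these are assumed: 15, 30 or 40% of control eyes clear, and uncleared eyes split 40/30/17/9/4% over 1/2+, 1+, 2+, 3+ and 4+. The treatment effect is one common odds ratio (OR) at every cut.

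**2. The plan's own figures.** The plan gives no power for the secondaries, so there is nothing to reproduce for them. The 74 per arm is taken as given, although it does not follow from its inputs: (1.96 + 0.84)² × (0.789×0.211 + 0.775×0.225) / 0.014² = 7.84 × 0.340854 / 0.000196 ≈ 13,600 per arm. That is a separate issue. The plan's rates imply OR = (0.789/0.211)/(0.775/0.225) ≈ 1.09.

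**3. One case by formula.** Take 30% of control eyes clear and OR 2.2. Test-arm odds = control odds × 2.2. Power ≈ Φ[(difference − 1.96·s0)/s1], where s0 and s1 are the pooled and unpooled standard errors at n = 74.

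- Cut at grade 0: 30.0% v 48.5%; (0.1853 − 1.96×0.0803)/0.0788 = 0.355, power 64%.
- Cut at 1/2+ or less: control 0.30 + 0.70×0.40 = 58.0%, test 75.2%; z = 0.268, power 61%.
- Cut at 1+ or less: 79.0% v 89.2%; z = −0.262, power 40%.

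**4. Simulation** (40,000 trials per cell, OR 2.2), power in %:

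| Control eyes clear | Grade 0 | 1/2+ or less | 1+ or less | 2+ or less | 3+ or less | Wilcoxon |
|---|---|---|---|---|---|---|
| 15% | 48.7 | 66.4 | 46.1 | 23.4 | 1.5 | 75.1 |
| 30% | 64.8 | 61.2 | 40.1 | 18.2 | 0.8 | 74.4 |
| 40% | 68.7 | 57.0 | 35.6 | 13.9 | 0.4 | 72.1 |
| 77.5% | 42.5 | 28.6 | 10.4 | 0.9 | 0.0 | 42.4 |

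The best cut moves with the distribution.

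**5. Sensitivity of the rank test's advantage.**

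- OR 1.5, Wilcoxon v best cut at 15/30/40% clear: 27.9 v 25.5, 27.6 v 22.6, 26.5 v 25.1.
- OR 1.09: no gain (5.8 to 6.0 v 6.2 to 6.8).
- 77.5% clear: no gain.
- Proportional odds dropped, so treatment changes clearance only (OR 2.2) and uncleared eyes keep the control split: the grade-0 table wins, about 65% v 54% at 30% clear and 68% v 60% at 40% clear.
- Other assumed distributions, OR 2.0: CCA at visit 1, cuts 4 to 58% v rank test 65%; CCA at visit 2, 0 to 58% v 59%; a five-grade scale, 4 to 54% v 64%.

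**6. No true effect.** Any one fixed cut rejects at about 5% or less, and Wilcoxon at about 5%. Taking the smallest p over five cuts gives 17.4, 16.5 and 16.2% at 15, 30 and 40% clear, about 13% at 60%, 11% at 77.5% and 9% at 85%. Choosing only between the two lowest cuts gives 8 to 10%.

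**7. A 0 to 4 symptom score.** OR 2.2, with 30/50/70% symptom-free and a 40/30/20/10% split above 0: Wilcoxon 75/68/51%, best cut 65/66/51%, worst cut 11/5/1%.

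**8. Centre, on the grade-0 primary.** Control rate 77.5%, OR 2 or 3, 3 to 10 centres. A centre-stratified Cochran-Mantel-Haenszel (CMH) test against the pooled test changes power by about −0.5 points with no centre effect, +0.4 to +0.8 at an assumed centre SD of 0.5, and +2.4 to +4.0 at SD 1.0. With no true effect, the pooled test rejects at 3.7 to 5.2%.

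**The case against.** Much of the case for the plan stands. Nothing in the documents says cuts will be chosen after results are seen, and one fixed cut is valid. The analysts are blinded. The outcomes are secondary. The power figures rest on distributions and odds ratios the plan does not supply, and a common odds ratio favours a rank test; step 5 shows that the sign of the advantage, not only its size, depends on it.

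Blinding answers only part of this. Section 8.3.1 says "The coding will be done using consecutive numbers for each intervention group", so two-sided p-values at each cut can be read without knowing which arm is which. That hinders favouring an arm but not searching for significance.

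Three stronger readings are tempting, and the documents do not support them:

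- A reader might infer that the secondaries will carry triple the nominal error. That needs an actual search over all five cuts with few eyes clear.
- A reader might infer that a rank test always has more power. It does not under clearance-only effects, at high clearance, or at the plan's own rates.
- A reader might infer that ignoring centre invalidates the primary. The pooled test after centre-balanced allocation is valid and at most conservative. That the tests are pooled is itself inferred from the absence of any stratification term.

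**Conclusion.** The concern holds as a weakness of prespecification and method for the ordinal secondaries, between and within groups. Under the stated assumptions (74 per arm, common OR 2.2, 15 to 40% of control eyes clear), the cut alone moves power between about 1% and 69%, against 72 to 75% for a whole-scale test. Error is about 5% with a fixed cut and about two to three times that (9 to 17%) if cuts are searched, lower when most eyes are clear. The firm argument for an ordinal test is that it needs no cut; the power gain is conditional on proportional odds.

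The point is worth correcting but does not touch the validity of the primary. It reads the ordinal rule in 8.3.1 as governing CCA. That section also mentions CCA under the continuous heading, and this contradiction must be settled first as a separate matter. Nothing here repairs the sample size in section 6.6.1, whose basis is a rate for difluprednate "compared to an efficiency ratio of 77.5% with the use of 1% prednisolone".

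**What to change.** Amend section 8.3.1 before any group-coded results are examined:

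1. Between groups, analyse CCA by visit, flare, corneal edema and hyperemia with one prespecified whole-scale test at named visits: either a centre-stratified Wilcoxon (van Elteren) test, or a proportional-odds model with baseline grade and centre. Within groups, replace McNemar on an unstated cut with a paired ordinal test (Wilcoxon signed-rank).
2. Apply the same rule to pain and photophobia, and state whether the severity or the frequency score is tested.
3. For any 2x2 table that is kept, fix the cut or the definition of decrease in advance, including how eyes at grade 0 at baseline are counted.
4. Optional and minor: stratify the grade-0 primary by centre with a CMH test, since allocation is balanced by centre. Expect about −0.5 to +0.8 points of power unless centres differ strongly.

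Cost: a protocol amendment with committee approval and regulatory authorization under section 10.2, but no new data. The downsides are that the power gain relies on proportional odds and that strata become sparse if centres are small.
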